## 17.0 Data Management\* and Confidentiality

### *17.1 Data Analysis Plan, including statistical procedures and power analysis*

Phase 1: Analysis of focus group data and most beta and usability testing will be done using qualitative methods and therefore is not subject to statistical considerations. Quantitative data in the beta and usability testing will use t-tests and Chi-square tests to examine differences, with a p-value of .05.

Phase II: We will calculate descriptive statistics for all variables. We will assess the quality of the data and evaluate the extent of missing data. If needed, we will address missing data issues by using multiple imputation methods; we will generate 10 multiple imputed datasets, analyze each separately, and then combine results across the 10 datasets. All statistical analyses will be performed as intention-to-treat (ITT) analyses. Given our use of administrative data to measure our primary outcomes, we will retain all women who consented and completed the baseline (N=1250). Assuming a 5% attrition rate from Group Health during the 12 months, we will use 1188 participants for our primary analyses (594/arm). For patient reported outcomes, we anticipate 10% attrition at 6 weeks and 10% attrition at 12 months, leaving 506/arm at 12 months. We will evaluate the associations

PROTOCOL TITLE:

ENGAGED2: ExperiNces with MammoGrAphy screeninG and brEast Density 2

between baseline variables, mediating variables assessed at 6 weeks, and 12 month outcomes. For categorical variables we will use Chi-Square tests or Fisher's exact tests if needed, while for continuous variables we will use Student t-tests or Wilcoxon-Mann-Whitney tests. Any variable that exhibits a  $p < .10$  association with outcomes of interest will be subsequently controlled for in analyses. We will assess attrition rates and subgroup effects over the short- and longer-term.

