Power calculations assume a two tailed  $\alpha = .05$  and  $N = 1188$  at 12 months (594/arm) for primary utilization outcomes of chemoprevention and MRI; calculations for patient-reported outcomes will assume  $N = 1012$  at 12 months (506/arm). To account for clustering by provider, we calculated effective sample sizes assuming an average cluster size of 11 patients/provider and intraclass correlation coefficient of 0.02. This reduces the sample size by a factor of 1.2, leaving effective sample sizes of 990 for utilization outcomes and 842 for patient-reported outcomes. We employ generalized estimation equations (GEE) methods with exchangeable working correlation structure to analyze clustered data.

Assess intervention effects on uptake and distress. 1a: Compared to UC, women in the PW arm will have higher rates of MRI and chemoprevention uptake at 12-months post-randomization. We will use logistic regression models with GEE to account for patients' clustered binary outcomes within their providers. We will use 2 separate logistic regression models for each binary outcome: chemoprevention and MRI uptake. These models will include intervention (PW vs. UC) as the main predictor, and baseline covariates as controlling variables. Given the effective sample size of 990, we provide a range of effect sizes that correspond to statistical power ranging from 80% to 99% in Table 5. UC rates are based on published uptake of chemoprevention and breast MRI. 1b: The intervention will not lead to increased distress compared with UC. To demonstrate that the PW arm does not result in greater distress than UC, we will test for noninferiority by constructing a one-sided 97.5% confidence limit for the adjusted (for baseline distress) mean difference between arms. Noninferiority will be demonstrated when the one-sided 97.5% confidence limit does not cross the noninferiority limit of 3 points. We arrived at this noninferiority limit based on outcomes among patients at increased cancer risk. Given the effective sample size of 842 we will have 80% power to conclude non-inferiority assuming a SD of 15.3 points. This reflects an extremely small effect size of  $< 0.20$ . 1c: Women in the PW arm will have higher rates of follow-up with providers to discuss MRI/chemoprevention. 1d: Women in the PW arm will have higher rates of mammography maintenance. We will use the approach in 1a for 1c and d.

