Identify mediators/moderators of intervention impact on uptake. 2a: Consistent with PMT, higher uptake of risk management in the PW arm will be mediated by increased perceptions of cancer threat (greater awareness of personal risk, higher perceived breast cancer risk, severity and worry) and stronger coping appraisals (higher response efficacy, lower response cost for preventive services; higher self-efficacy). To increase power we will use the product of coefficients method to

PROTOCOL TITLE:

ENGAGED2: ExperiencEs with MammoGrAphy screeninG and brEast Density 2

evaluate mediation effects. Using logistic regression models with GEE we will estimate the standardized coefficients relating each mediating variable (e.g. worry) to the chemoprevention and MRI uptake outcomes ( $\beta$ ), and the standardized coefficients relating the intervention (PW vs. UC) to the mediating variables ( $\alpha$ ). These models will control for the baseline measurement of the mediator variable and also other baseline covariates. We will then calculate each mediated effect as the corresponding product of these coefficients ( $\alpha\beta$ ) with its standard error and 95% confidence interval estimated as described by MacKinnon. Effect sizes of 0.14, 0.39 and 0.59 for the coefficient parameters are considered “small”, “medium” and “large” respectively. We will be able to detect a mediation effect (coefficient product) of small size (with coefficient product parameters  $\alpha = 0.14$ ,  $\beta = 0.14$ ) at >95% power for each mediator, given our total effective sample size of 842.

Given our incorporation of intervention elements supporting patient comprehension, values clarification and communication, we anticipate that PW participants will have similar rates of risk management regardless of literacy/numeracy level. In contrast, we expect lower uptake of risk management options among UC participants with lower literacy/numeracy. However, even with our large sample, we are underpowered to detect this subtle moderation effect. Therefore, we will examine these relationships in exploratory subgroup analyses. We also will assess the robustness of outcomes across patient subgroups using additional, exploratory moderation analyses. Given our individual focus, we will examine adoption by patients, but explore whether effects are moderated by clinical variables (i.e., mammography facilities, primary care clinic home).

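### Section 17.1 must reconcile an outcome-driven p<.10 covariate rule, which does not exclude 6-week mediators, with the unnamed baseline covariates of the Aim 1a, 1c and 1d models

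*Combined protocol and SAP*

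**What the plan says.** Both statements are in section 17.1.

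- **General rule for Phase II.** The plan will evaluate associations "between baseline variables, mediating variables assessed at 6 weeks, and 12 month outcomes". After a sentence on which tests to use, it says that any variable with a p<.10 "association with outcomes of interest will be subsequently controlled for in analyses". The rule is not limited to baseline variables, does not say which outcomes are meant, and does not say which analyses it covers.
- **Aim 1a.** "We will use 2 separate logistic regression models for each binary outcome: chemoprevention and MRI uptake". Their content is then given: "These models will include intervention (PW vs. UC) as the main predictor, and baseline covariates as controlling variables". No covariate is named and no selection method is stated.
- **Aims 1c and 1d.** "We will use the approach in 1a for 1c and d".

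Aim 1b names its adjuster, baseline distress. Aim 2a has separate mediation models. Table 1 in section 6.4 lists measures by timepoint but does not mark any as a model covariate.

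**The concern.** The p<.10 rule is the only selection rule in the plan, so it is the natural way to fill the unnamed baseline set. Two difficulties follow.

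First, the primary model cannot be written down until 12-month outcomes have been examined. With two separate 1a models, it is also open whether the screen runs per outcome or across outcomes.

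Second, the general rule taken alone covers 6-week mediators. Hypothesis 2a in section 2.2 expects perceived threat and coping appraisals to carry the intervention's effect on uptake. Adjusting the 1a model for such a variable would remove the part of the effect that passes through it. The arm coefficient would then be a direct effect, whereas hypothesis 1a concerns the total effect.

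**Working it through.** **1. The plan's own sample sizes.** Inputs are from section 17.1.

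- Utilization outcomes: 1250 × 0.95 = 1187.5, stated as 1188. The design effect is 1 + (11 − 1) × 0.02 = 1.2, and 1188 / 1.2 = 990, as stated.
- Patient-reported outcomes: 625 × 0.9 × 0.9 = 506.25 per arm, stated as 506. 1012 / 1.2 = 843.3, against 842 stated.

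These reproduce, and none is in dispute.

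**2. Which reading the plan favours.** The Aim 1a text says baseline. The sizes agree: the plan says "we will use 1188 participants for our primary analyses (594/arm"), while for survey data "we anticipate 10% attrition at 6 weeks and 10% attrition at 12 months, leaving 506/arm at 12 months". Women with 6-week data would number 1250 × 0.9 = 1125. A 1a model containing 6-week variables could therefore not use 1188 women without imputing those variables. Mediation is planned separately, "given our total effective sample size of 842". Two limits apply: the plan does allow multiple imputation, and the argument does not carry to 1c if that outcome is the patient-reported provider discussion in Table 1.

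**3. What the general rule would reach.** Table 1 has 10 mediator rows measured at 6 weeks. Five have no baseline value: chemoprevention intentions, MRI intentions, self-efficacy, response cost and response efficacy. For these, the screen could use only a post-randomisation value.

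**4. Baseline-only reading.** Simulation with 495 per arm (effective N 990) and a two-sided 5% test; clustering enters only through the effective N. Assumed uptake: chemoprevention UC 2% and PW 5.5%; MRI UC 5% and PW 9.7% (each about 80% power). There are 18 candidate covariates, one per baseline row of Table 1. This is illustrative, since a row is not a variable. Either none or four are prognostic (log-odds 0.3 per SD). The fixed list holds three of the four prognostic variables, or nothing when none is prognostic. 3000 runs; entries are fixed list / p<.10 screen.

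| Correlation, prognostic | Type I, chemo | Type I, MRI | Power, chemo | Power, MRI |
|---|---|---|---|---|
| 0, none | 0.040 / 0.041 | 0.048 / 0.050 | 0.830 / 0.829 | 0.822 / 0.818 |
| 0, four | 0.039 / 0.039 | 0.051 / 0.051 | 0.824 / 0.819 | 0.805 / 0.799 |
| 0.3, none | 0.037 / 0.037 | 0.050 / 0.050 | 0.834 / 0.834 | 0.802 / 0.801 |
| 0.3, four | 0.041 / 0.045 | 0.053 / 0.057 | 0.842 / 0.849 | 0.835 / 0.833 |

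Power differs by less than 1 point throughout. The significance call differs between the two approaches in 0.3% to 3.0% of trials.

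**5. Literal reading, one mediator.** The path size is 0.14, which section 17.1 calls small and uses for its mediation power.

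- Arm to mediator: as a standardised coefficient with 1:1 allocation (SD of the arm indicator 0.5), 0.14 / 0.5 = 0.28 SD between arms. Read directly as an arm difference, it is 0.14 SD.
- Mediator to uptake: 0.14 log-odds per SD if raw, or 0.14 × π/√3 = 0.254 if standardised.

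Assumed uptake, UC to PW: 2% to 5.5%, 5% to 9.7%, 10% to 16.0%. 6000 runs; entries are unadjusted power → power after screening and adjusting.

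| Arm difference, log-odds per SD | UC 2% | UC 5% | UC 10% |
|---|---|---|---|
| 0.28 SD, 0.14 | 0.829 → 0.808 | 0.805 → 0.765 | 0.804 → 0.750 |
| 0.28 SD, 0.254 | 0.836 → 0.782 | 0.812 → 0.729 | 0.794 → 0.678 |
| 0.14 SD, 0.14 | 0.830 → 0.821 | 0.810 → 0.793 | 0.807 → 0.787 |
| 0.14 SD, 0.254 | 0.841 → 0.821 | 0.821 → 0.781 | 0.792 → 0.740 |

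Losses in points at UC 2%, 5% and 10%: with 0.28 SD, 2, 4 and 5 (raw) or 5, 8 and 12 (standardised); with 0.14 SD, 1 to 2 (raw) or 2 to 5 (standardised).

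Hand check at UC 5%, 0.28 SD, 0.254: the total log odds ratio is ln(0.097/0.903) − ln(0.05/0.95) = 0.713. The mediated part is 0.28 × 0.254 = 0.071, or 10% of the total. The simulated log odds ratio shrank to 0.910 of its unadjusted value. That is slightly less shrinkage than 10%, because the screen does not always select the mediator.

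**The case against.** The strongest reply is that the Aim 1a text already says what the models contain. A 6-week variable is not a baseline covariate, 1c and 1d inherit that description, and mediators have their own models. This largely stands. It makes baseline-only the likelier reading, and it would be wrong to say that the plan never keeps mediators out of the Aim 1 models. What remains is that the general rule is broader, is still in force, and is not tied to the Aim 1a text.

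The second reply is that, on the likelier reading, nothing measurable is lost. That also stands. A reader might infer that screening on outcomes inflates type I error; the simulation does not support this.

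A reader might also treat instability of the selected set as harm. In the same simulation the chemoprevention and MRI models received different covariates in 93% to 99.7% of trials. But models of two different outcomes may properly carry different covariates, and with 18 independent noise candidates identical sets would arise only 0.82^18 = 2.8% of the time. That figure does not measure damage.

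Finally, the uptake rates are assumed. The 12-point loss needs the less likely reading, UC 10%, the larger arm difference and the standardised scale all together. Aims 1c and 1d were not simulated.

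**Conclusion.** The point holds as a matter of specification. Section 17.1 leaves the covariates of the 1a, 1c and 1d models unnamed, offers only an outcome-driven rule for choosing them, and words that rule more broadly than the Aim 1a text. That the covariates are unnamed and the rule outcome-driven is plain on the page.

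On the likelier baseline-only reading, the effect on type I error and power is negligible. The harm is that nobody can verify that the reported primary model was the planned one. On the literal reading of the general rule, the total effect is biased toward the null; the cost is about 2 to 12 points of power with a 0.28 SD arm difference and 1 to 5 points with 0.14 SD. Those losses rest on assumed uptake rates, one mediator of the plan's small size and an effective N of 990. The documents do not support saying that mediators will be adjusted for in the primary analysis, only that the wording leaves room for it. The plan should be corrected, but the primary result is not shown to be under threat.

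**What to change.** In section 17.1, for Aim 1:

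- Remove the p<.10 rule, or limit it to descriptive use.
- For 1a, 1c and 1d, name a short list of baseline covariates, fixed before outcomes are examined. Examples are the eligibility risk/density group, age, and baseline status of the same outcome where it is not too sparse. The choice is the study team's.
- Keep baseline distress for 1b as already stated.
- State that no post-randomisation variable enters the Aim 1 models and that 6-week mediators are used only in the Aim 2 models.

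This is wording only and needs no new data or change in sample size. The team gives up choosing covariates after seeing outcomes, and a prognostic variable may be left off. In the simulation a list that omitted one of four prognostic variables kept power within 1 point of the screened model. That was a favourable case, and it does not validate the example list above; a sparse binary baseline covariate was not tested.

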**6.4 Measures are summarized in Table 1:**

Study Measures			
Variable	Timepoint		
	Baseline	6-wk.	12-mo.
Sociodemographics	X		
Medical/Screening Variables	X		X
Plan coverage	X		X
Health-system level variables	X		X
Outcomes			
Healthcare utilization			
Chemoprevention uptake	X		X
MRI uptake	X		X
Mammography uptake	X		X
Healthcare utilization	X		X
Patient-reported outcomes			
Distress (IES)	X	X	X
Patient-provider discussion	X		X
Mediators			
Mammography/CBE intentions	X	X	X
Chemoprevention intentions		X	X
MRI intentions		X	X
Awareness of breast cancer risk	X	X	X
Perceived breast cancer severity	X	X	X
Perceived breast cancer risk	X	X	X
Breast cancer worry	X	X	X
Self-efficacy: Chemoprevention, MRI		X	X
Response cost: Chemoprevention, MRI		X	X
Response efficacy: Chemoprevention, MRI		X	X
Moderators			
Health literacy (Chew et al.)	X		
eHealth literacy (eHEALS)	X		
Numeracy (SNS)	X		

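### The Aim 2 mediation power of over 95% matches two linear paths, but uptake is modelled by logistic GEE, where power depends on an unstated uptake rate and scale

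*Combined protocol and SAP*

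**What the plan says.** All of this is in section 17.1 of the combined protocol and SAP, unless noted.

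- **Outcome path (beta).** "Using logistic regression models with GEE we will estimate the standardized coefficients relating each mediating variable" to chemoprevention and MRI uptake. Both outcomes are binary: for Aim 1 the plan says "We will use 2 separate logistic regression models for each binary outcome: chemoprevention and MRI uptake".
- **Intervention path (alpha).** The plan will also estimate "the standardized coefficients relating the intervention (PW vs. UC) to the mediating variables".
- **Test.** "We will then calculate each mediated effect as the corresponding product of these coefficients", with a standard error and 95% confidence interval taken from a cited methods source.
- **Benchmarks.** "Effect sizes of 0.14, 0.39 and 0.59 for the coefficient parameters are considered" small, medium and large.
- **Power.** With alpha = beta = 0.14 and a total effective sample of 842, the small effect is said to be detectable "at >95% power for each mediator".
- **Adjustment.** "These models will control for the baseline measurement of the mediator variable" and for other baseline covariates.

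The mediation power statement gives no uptake rate. For Aim 1, the same section refers to published usual-care rates and to Table 5, which is not in the available text. Section 3.0 describes chemoprevention use in the population and MRI uptake among high-risk women as low, without a figure.

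**The concern.** For a linear outcome path, a standardized coefficient and a sample size are enough to fix the power. For a logistic path they are not. The information on a log-odds coefficient is proportional to p(1−p), where p is the proportion with uptake, so the same coefficient is estimated much less precisely when uptake is rare. The text does call both paths standardized, but that word has several meanings for a logistic coefficient, and for a 0/1 arm indicator.

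At stake is how a null mediation result would be read. Hypothesis 2a tests the theory behind the intervention. A reader who trusts a power above 95% for a small effect would take a null result as evidence against that mediator. If uptake is low, the trial may have been able to detect only a fairly strong mediator-uptake association.

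**Working it through.** **Inputs from section 17.1.** alpha = beta = 0.14; effective N = 842; two-sided 5% level. Randomization is 1:1 (section 5.2). The 842 already allows for clustering, so observations are treated as independent.

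**Assumption.** Pooled 12-month uptake p is set at 2%, 5%, 10%, 20% and 50%. The first four correspond to about 17, 42, 84 and 168 users among 842.

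**Step 1: reproduce the plan's figure.** With both paths linear and standardized, SE ≈ 1/√842.
- z = 0.14 × √842 = 4.062 for each path.
- Power per path = Φ(4.062 − 1.96) = 0.982.
- Joint power = 0.982² = 0.965.
- Simulation gives 0.963 to 0.966 with a distribution-of-product or Monte Carlo interval.
- A normal-theory test of the product gives z = 4.062/√2 = 2.873 and power 0.82 in closed form (about 0.92 to 0.93 simulated), so it does not reproduce the claim.

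**Step 2: logistic beta path, alpha still a correlation of 0.14 (path power 0.982).**
- SE(b) = 1/√(842 × p × (1−p)).
- Latent-logistic scale: b = 0.14/√(1 − 0.14²) × π/√3 = 0.256, an odds ratio of 1.29 per SD.
- Joint power = Φ(b/SE − 1.96) × 0.982.
- Example at p = 10%: SE = 1/√(842 × 0.09) = 0.115; z = 0.256/0.115 = 2.23; path power 0.607; joint power 0.607 × 0.982 = 0.60.

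| Assumed uptake | Latent scale, closed form | Latent scale, simulated | Beta as correlation: joint power | Beta as correlation: OR per SD |
|---|---|---|---|---|
| 2% | 18% | 18% | 96% | 2.8 |
| 5% | 36% | 36% | 96% | 1.9 |
| 10% | 60% | 59% | 96% | 1.6 |
| 20% | 83% | 82% | 96% | 1.4 |
| 50% | 94% | 94% | 96% | 1.3 |

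For the correlation columns, b is solved so that the correlation between mediator and binary uptake is 0.14, and its SE comes from the logistic information matrix.

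**Step 3: the scale of alpha.** A correlation of 0.14 with a 1:1 arm indicator is a between-arm difference of 2 × 0.14/√(1 − 0.14²) ≈ 0.28 mediator SD. If 0.14 is instead the between-arm difference in SDs, then z = 0.14/(2/√842) = 2.03 and power = Φ(2.03 − 1.96) = 0.53 before covariate adjustment. Joint power cannot exceed that. Adjusting for a baseline measure correlated 0.5 or 0.7 with the mediator (assumed values) raises the 0.53 to 0.65 or 0.81. In Table 1 of section 6.4, the rows "Self-efficacy: Chemoprevention, MRI", response cost and response efficacy have no baseline entry.

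**Step 4: sensitivity to N.** Mediators are assessed at 6 weeks and uptake is administrative, so 1250 × 0.9/1.2 ≈ 937 could be argued. Latent-scale joint power is then 65% at 10% uptake and 96% at 40%. At N = 990 it is 20%, 42%, 67% and 89% at 2%, 5%, 10% and 20%.

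**The case against.** The plan's figure follows from its own inputs, so nothing has been miscalculated. Both paths are called standardized, and on a fully standardized, correlation-type reading the power stays near 96% at every uptake rate. The sources cited for the benchmarks, the interval and the power may define the scale, and Table 5 may hold the usual-care rates. Neither can be seen here, and neither is counted as missing. The 2% to 20% range is assumed. Section 3.0 gives no number and does not describe trial participants, half of whom receive an intervention meant to raise uptake. At 50% uptake the latent-scale shortfall is about one point, and at N near 937 the figure is reached once uptake is about 40%.

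All of this stands, and it rules out some stronger readings:

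- **That the claim is simply false.** A reader might infer that power above 95% is not reached. The documents do not support that without a condition on scale and uptake.
- **That power is as low as 9% to 36%.** Reading beta as 0.14 log-odds per SD gives about 9%, 14%, 23% and 36% at 2%, 5%, 10% and 20% uptake. That standardizes only the mediator and is the least favourable reading of the text.
- **That joint power is capped at 53%.** This needs alpha to be a raw difference with the arm indicator left unstandardized. It also ignores the other baseline covariates, which could help even mediators with no baseline measure.

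The objection does not show that the stated power applies to the planned logistic coefficient when uptake is low. On the latent scale, neither 937 nor 990 brings power near 95% at 10% uptake. The correlation reading keeps the figure only by making 0.14 an odds ratio of 1.6 to 2.8 per SD at 2% to 10% uptake, which is hard to call small.

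**Conclusion.** The point holds in conditional form. The stated power is the power of two linear standardized paths, while the planned outcome path is logistic on a binary outcome, and the text does not say how 0.14 carries over. With alpha as a correlation, N = 842 and latent-logistic beta, joint power is about 18%, 36%, 59% and 82% at assumed uptake of 2%, 5%, 10% and 20%. The shortfall is large at about 10% and below, and marginal at 50%.

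These sizes rest on assumed rates, on closed forms and simulations without covariates beyond arm, and on taking the 842 as fully adjusted for clustering. The consequence is limited to Aim 2: Aim 1, the sample size and the analysis method are unaffected, and the planned 95% intervals would show the imprecision. A reader should not infer that the trial as a whole is underpowered. The statement should be corrected, but it does not threaten the primary analysis.

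**What to change.** In section 17.1, replace the mediation power claim in one of two ways.

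1. **Recalculate.** Give power for the logistic outcome path at the chemoprevention and MRI uptake rates used for Aim 1, using the planned product-of-coefficients interval. State the scale of both alpha and beta.
2. **State the smallest detectable effect.** For example: with effective N = 842, an intervention-mediator correlation of 0.14 (about 0.28 mediator SD between arms) and pooled uptake of X%, the 95% interval for the product has 80% power to exclude zero if the mediator-uptake odds ratio is Y per SD. With a distribution-of-product interval, Y is about 2.1, 1.6, 1.4 and 1.3 at X = 2, 5, 10 and 20 (closed form for joint significance: 2.02, 1.57, 1.39 and 1.28).

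If 0.14 was meant as a between-arm difference in SDs, say so and recalculate with the covariate adjustment actually available for each mediator. Without adjustment, 80% is out of reach because the alpha path alone has about 53%.

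The cost is one recalculation and one or two sentences, with a less favourable stated power as the only downside. No extra patients are needed and the analysis method does not change.
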